8.4.1.2 At Least 35% Reduction in Spleen Volume from Baseline (SVR₃₅)

SVR₃₅ rate is defined as the proportion of subjects who achieve at least 35% reduction in spleen volume from baseline at any time during the study. Subjects who do not have any post-baseline spleen volume assessment or who have had confirmed disease progression or started post-study treatment prior to achieving SVR₃₅ will be treated as non-responders. Subjects who do not receive any study drug will be treated as non-responders. Subjects

without baseline spleen volume assessment or with unevaluable baseline spleen volume will be treated as non-responders.

SVR₃₅ rate will be analyzed using the statistical method described for binary variables in Section 8.1. In addition, descriptive summaries of spleen volume and percent change from baseline at each visit will be provided for each treatment arm and will be presented graphically. Maximum percent reduction from baseline will also be presented graphically for each treatment arm. Time to first SVR₃₅ will be descriptively summarized for each treatment arm. The proportion of subjects who achieve at least 35% reduction in spleen volume from baseline at Week 12 will be descriptively summarized for each treatment arm.

8.4.1.3 Change in Fatigue from Baseline at Week 24

Patient reported outcome on fatigue will be assessed using the global fatigue score as measured by PROMIS Cancer Fatigue SF 7a.⁴ Scores will be computed according to the PROMIS Cancer Fatigue SF 7a scoring manual. All questions must be answered to calculate the total score. Change in scores from baseline at Week 24 will be compared between the treatment arms using the linear mixed effects model described in Section 8.1. The tipping point analysis described in Section 8.2 will be performed as sensitivity analyses. T-scores will be used in the analysis.

8.4.1.4 Anemia Response

Definition of Baseline Transfusion Dependence

Baseline transfusion dependence (TD) is defined as transfusion of at least 6 units of packed red blood cells (PRBC) within 12 weeks on or prior to the date of the first dose of study drug (or randomization for untreated subjects). In addition, the most recent transfusion episode must have occurred within 4 weeks on or prior to the date of the first dose of study drug (or randomization for untreated subjects). Subjects with baseline hemoglobin level of < 10 g/dL who do not meet the criteria for baseline transfusion dependence are considered baseline transfusion independent (TI).

Definition of Baseline Hemoglobin

For subjects who receive PRBC transfusion within 4 weeks on or prior to the date of the first dose of study drug (or randomization for untreated subjects), the baseline hemoglobin value is defined as the minimum of the hemoglobin value collected prior to the transfusion, if available, and the last non-missing hemoglobin value on or prior to the date of the first dose of study drug (or randomization for untreated subjects).

For subjects who do not receive PRBC transfusion within 4 weeks on or prior to the date of the first dose of study drug (or randomization for untreated subjects), the baseline hemoglobin value is defined as the last non-missing hemoglobin value on or prior to the date of the first dose of study drug (or randomization for untreated subjects).

Definition of Anemia Response

For subjects who are baseline transfusion independent and whose baseline hemoglobin is < 10 g/dL, anemia response is defined as ≥ 2 g/dL increase in hemoglobin from baseline without receiving any PRBC transfusion within 2 weeks or erythropoietin supplements within 4 weeks. Hemoglobin values after the last dose + 30 days, confirmed disease progression or start of post-study treatment will not be considered in the analysis of anemia response.

For subjects who are baseline transfusion dependent, anemia response is defined as a period of at least 12 consecutive weeks without PRBC transfusion after the first dose of study drug until the last dose + 30 days, start of post-study treatment, confirmed disease progression or death, which occurs earlier.

Subjects who do not receive any study drug will be treated as non-responders. Subjects who are baseline transfusion independent and whose baseline hemoglobin is ≥ 10 g/dL will not be included in the analysis since these subjects are not applicable to the evaluation of anemia response.

Anemia response rate is defined as the proportion of subjects who achieve anemia response and will be analyzed using the statistical method described for binary variables in Section 8.1. The main analysis of anemia response will include both TD and TI subjects, with separate summaries provided for TD and TI subjects.

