5.9 Study Drug

Navitoclax and matching placebo will be provided by the Sponsor as film-coated tablets (25 mg and 100 mg) for oral administration taken once daily in the morning. Tablets must be taken with water within approximately 30 minutes after the completion of a meal. Tablets must be swallowed whole and

must not be broken, chewed, or crushed. If the subject misses a dose of navitoclax/placebo, the missed dose should be taken with food and water within 8 hours of the scheduled dose time. After 8 hours, the missed dose should not be taken and the next dose of navitoclax/placebo will be at the next scheduled dosing time.

If the subject vomits following dosing, no additional dose should be taken that day. The next prescribed dose of navitoclax/placebo should be taken at the usual time the following day.

Ruxolitinib tablets will be provided by AbbVie or sourced locally by the sites, depending on country regulations. Ruxolitinib should be taken orally twice daily at approximately the same time each day, once in the morning (at the same time as navitoclax, if applicable) and once in the evening, approximately 12 hours later. The absorption of ruxolitinib is not affected by food and ruxolitinib may be taken with or without food. If the subject misses a dose of ruxolitinib, the subject should take the next dose at the scheduled time. The subject should not take 2 doses at the same time.

Each kit will be labeled per local requirements and this label must remain affixed to the kit. Upon receipt, study drug should be stored as specified on the label and kept in a secure location. Each kit will contain a unique kit number. This kit number is assigned to a subject via interactive response technology (IRT) and encodes the appropriate study drug to be dispensed at the subject's corresponding study visit. Site staff will complete all blank spaces on the label before dispensing to subjects. Study drug will only be used for the conduct of this study.

If a subject is unable to come to the study site to pick up their study drug due to COVID-19, a direct-to-patient (DTP) study drug shipment can be made from the study site to the subject if allowed by local regulations. AbbVie will submit any required notifications to the regulatory authority as applicable. Refer to the Operations Manual in [Appendix I](#) for details on DTP shipment of study drug.

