Navitoclax accelerates apoptosis of circulating mature platelets whether endogenous or transfused. This mechanism of toxicity differs from the thrombocytopenia caused by ruxolitinib and other conventional chemotherapy (i.e., toxicity to platelet progenitors in the bone marrow) and should, therefore, be managed according to the guidelines provided in [Table 1](#), unless previously discussed and approved with the AbbVie TA MD/SD.

Hematology samples must be collected within 24 hours prior to the first dose of study drug to determine dose of study drug, at 4 hours after the first dose of study treatment, and on Day 2 (see Activity Schedule, [Appendix D](#), and Operations Manual, Section 3.14). The investigator should consider additional hematology labs on Day 3 and/or Day 4 for subjects with a lower baseline platelet count and for subjects who experience a > 40% decrease in platelet count on Day 2 from the pre-dose platelet count. Additional hematology labs may be performed based on platelet counts as medically indicated at the investigator's discretion.

Any Grade ≥ 2 bleeding event (regardless of platelet count) will require interruption of dosing. Upon resolution of a Grade ≥ 2 bleeding event, study drug treatment may be reintroduced at the same or lower dose level (in consultation with the AbbVie TA MD/SD), provided the patient is asymptomatic with no evidence of an active bleeding.

If platelet transfusions are required in response to active bleeding, navitoclax/placebo dosing should be interrupted. It should be noted that platelet response with transfusions may not follow typical platelet kinetics of thrombocytopenia as with typical chemotherapy-induced thrombocytopenia. Procedures consistent with local institutional blood banking guidelines regarding platelet transfusions should be followed.

Platelet Transfusion Recommendations:

If platelet transfusion is deemed necessary, the treating physician should be aware that due to the rapid apoptotic effect of navitoclax on mature platelets, the increase in platelet counts post-transfusion may be lower and the duration of response may be shorter. Therefore, donor platelets collected as recently as possible prior to transfusion should be used. Additional transfusions may be necessary to achieve the desired platelet count. Post-transfusion platelet count monitoring should include:

- A platelet count obtained 10 to 60 minutes post transfusion.

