7.1 Demographics and Baseline Characteristics

All baseline characteristic summary statistics and analyses are based on characteristics prior to the first dose of study drug or date of randomization for untreated subjects.

Distributions of the continuous demographic and baseline characteristic variables will be summarized by treatment arms with the number of non-missing observations, mean, standard deviation, and median, as well as the minimum and maximum values.

For the categorical demographic and baseline characteristic variables, the frequency and percentages of subjects within each category will be summarized by treatment arms. The number of subjects with missing information will also be summarized.

The following demographic and baseline characteristics will be summarized:

Demographics

- Age (years) and Age Categories (18 - < 65, 65 - < 75, ≥ 75 years)
- Gender (Male, Female)
- Race (White, Black or African American, Asian, Other)
- Ethnicity (Hispanic or Latino, Not Hispanic or Latino)
- Region (US, Europe, Japan, Other Regions)
- Height (cm)
- Weight (kg)
- Body Mass Index (kg/m²)

Baseline and Disease-Related Characteristics

- DIPSS+ Risk Group Reported in IRT (Intermediate-2, High)
- DIPSS+ Risk Group Reported in EDC (Intermediate-1, Intermediate-2, High)

- Platelet Count Reported in IRT ($\leq 200 \times 10^9/L$, $> 200 \times 10^9/L$)
- Baseline Platelet Count ($\leq 200 \times 10^9/L$, $> 200 \times 10^9/L$)
- Type of Myelofibrosis (Primary Myelofibrosis, Secondary Myelofibrosis)
 - Type of Secondary Myelofibrosis (Post-Polycythemia Vera Myelofibrosis, Post-Essential Thrombocythemia Myelofibrosis)
- JAK2 V617F Mutation (Detected, Not Detected)
- CALR Frameshift Mutation (Detected, Not Detected)
- MPL W515 Mutation (Detected, Not Detected)
- Negative of JAK2, CALR and MPL (Yes, No)
- High Molecular Risk (Yes, No)
- Time Since Myelofibrosis Diagnosis (months)
- Number of Prior Lines of Therapies for Myelofibrosis
- Reasons for Change of Therapy (Splenomegaly, Worsening Symptoms, Increased Need for Transfusion, Anemia, Thrombocytopenia, Increasing WBC, Increasing LDH, Other)
- Baseline ECOG Performance Status (0, 1, 2)
- Baseline Spleen Length by Palpation (cm)
- Baseline Spleen Volume (cm^3)
- Baseline TSS score
- Baseline Bone Marrow Fibrosis Grade (MF-0, MF-1, MF-2, MF-3)
- Baseline Transfusion Dependent (Yes, No)
- Baseline Hemoglobin (g/dL)
- Baseline CTCAE Grade of Anemia
- Baseline Platelet Count ($10^9/L$)

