Unless otherwise specified, time-to-event endpoints will be analyzed using Kaplan-Meier methodology and compared between treatment arms using the log-rank test, stratified by DIPSS+ risk group (intermediate versus high risk) and platelet count ($\leq 200 \times 10^9/L$ versus $> 200 \times 10^9/L$). The hazard ratio between treatment arms and the corresponding 95% confidence interval will be estimated using the Cox proportional hazards model, stratified by DIPSS+ risk group (intermediate versus high risk) and platelet count ($\leq 200 \times 10^9/L$ versus $> 200 \times 10^9/L$).

Unless otherwise specified, if a subject prematurely breaks the blind, data after the blind break will be included in the statistical analysis as appropriate based on the definition and analysis of the efficacy endpoints.

Unless otherwise specified, baseline refers to the last non-missing observation before the first administration of study drug or randomization if no study drug is given.

Unless otherwise specified, a confirmed disease progression is defined as any of the following:

- Two consecutive disease responses of progressive disease or relapse, in which case the date of the confirmed disease progression will be the date of the first progressive disease or relapse

- A progressive disease due to leukemic transformation
- A progressive disease or relapse that is the last disease response of a subject.

At the time this SAP is written, the evidence-based MCT for change from baseline in TSS at Week 24 is determined to be –10.

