9.3 Analysis of Laboratory Data

Data collected from central and local laboratories, including additional laboratory testing due to an SAE, will be used in all analyses. Change from baseline will be summarized and presented for key lab parameters at scheduled post-baseline visits. Baseline is defined as the last non-missing observation before the first dose of study drug or randomization if no study drug is given.

For shifts relative to National Cancer Institute Common Toxicity Criteria for Adverse Events, baseline and post-baseline laboratory observations will be categorized as Grade 0, Grade 1, Grade 2, Grade 3, or Grade 4 according to NCI CTCAE grading. The baseline grade is defined as the grade of the last measurement collected on or prior to the first dose of study drug (or randomization for non-treated subjects). In cases where multiple values are collected on the same day, the maximum grade value will be selected as the value for that day for post-baseline values and the minimum grade will be selected as the value for that day for baseline values. If a subject had missing baseline and non-missing post-baseline for a given lab, the baseline grade will be assumed to be Grade 0. The maximum NCI toxicity grade value is the value with highest NCI toxicity grade collected after the first dose of study drug.

For each variable, cross tabulation tables will be generated that cross tabulate the number of subjects with baseline values of Grade 0, Grade 1, Grade 2, Grade 3, or Grade 4 versus maximum post-baseline values of Grade 0, Grade 1, Grade 2, Grade 3, or Grade 4. Subjects with missing measurements will be counted in the "missing" category. All treated subjects will be included in the cross tabulation regardless of whether baseline or post-baseline measurements are collected.

The laboratory shifts tables based on the two criteria below will be generated for each laboratory tests related to CTCAE:

1. Shifts from Grade 0 (Normal) at baseline to Grade 1 - 4 post-baseline (maximum) and worsening from an abnormal baseline value of at least one grade up post-baseline (maximum).
2. Shifts from Grade 0 - 2 at baseline to Grade 3 or 4 post-baseline (maximum) and from Grade 3 at baseline value to Grade 4 post-baseline (maximum).

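### As written, the date-based baseline hemoglobin rule in SAP 8.4.1.4 admits the mandatory 4-hour post-dose sample as baseline for the ranked anemia endpoint

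*SAP*

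**What the plan says.** SAP 8.4.1.4 has two baseline hemoglobin definitions. For subjects with no red cell transfusion in the preceding 4 weeks, baseline is "the last non-missing hemoglobin value on or prior to the date of the first dose of study drug" (randomization for untreated subjects). For subjects transfused in that window, it is the smaller of the pre-transfusion value, if there is one, and a last value chosen by the same date rule.

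The Protocol fixes the samples around the first dose. Section 6.2 states: "Hematology samples must be collected within 24 hours prior to the first dose of study drug to determine dose of study drug, at 4 hours". The post-dose draws are "at 4 hours after the first dose of study treatment, and on Day 2", so the 4-hour draw is listed separately from Day 2. Section 5.9 describes navitoclax/placebo tablets "for oral administration taken once daily in the morning", with the morning ruxolitinib dose at the same time.

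Elsewhere the SAP uses a pre-dose baseline. Section 8.1 says that, unless otherwise specified, "baseline refers to the last non-missing observation before the first administration of study drug or randomization if no study drug is given". Section 7.1, which lists baseline hemoglobin among its variables, says the summaries are "based on characteristics prior to the first dose of study drug or date of randomization for untreated subjects".

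**The concern.** A baseline should come before treatment. Under the date rule, a subject who follows the Protocol has a hemoglobin value on the first-dose date that was drawn after the dose, and that value is the last one on the date.

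The value is used twice. Non-transfusion-dependent subjects enter the anemia analysis only if baseline hemoglobin is below 10 g/dL, so membership of the analysis set would rest on a measurement made after randomization and after dosing. The same value is the reference for the required rise of at least 2 g/dL.

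Anemia response is fourth in SAP Table 1, tested at two-sided 0.05. Fibrosis, OS, LFS, fatigue and physical functioning all come after it. The baseline hemoglobin in the demographics table (7.1) could also differ from the one used for the endpoint in the same subject.

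**Working it through.** The plan gives no figure for this point, so there is none to reproduce. The check is textual, followed by an illustration of size.

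**1. Order of samples.** Pre-dose draw (within 24 hours before the dose, possibly the previous day); first dose, in the morning; 4-hour draw, same calendar date; Day 2 draw.

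**2. Each rule applied to that order.**

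| Rule | Limit | Sample selected |
|---|---|---|
| SAP 8.1 | before first administration | pre-dose |
| SAP 7.1 | prior to first dose | pre-dose |
| SAP 8.4.1.4 | on or before the first-dose date | 4-hour, if non-missing |

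**3. Does the general rule prevent this?** No. Section 8.1 gives way where something else is specified, and 8.4.1.4 does specify something else. Nothing in 8.4.1.4 excludes post-dose values or sets an order among values from the same day.

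**4. Who is affected.**
- Transfusion-dependent subjects: not affected. They enter whatever their hemoglobin, and their response is 12 weeks without transfusion.
- Not transfusion-dependent, transfused within 4 weeks: affected only if the 4-hour value is the lower one or there is no pre-transfusion value.
- Not transfusion-dependent, no transfusion within 4 weeks: affected whenever the 4-hour hemoglobin is recorded.

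**5. Illustrative size at the 10 g/dL line.** All inputs here are assumptions; none is in the documents. Pre-dose hemoglobin is normal with mean m = 10.5 or 11 and SD 2 g/dL. The 4-hour minus pre-dose difference is normal with mean 0 and SD s = 0.2 or 0.5 g/dL.

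Share changing sides ≈ f(10) × E|D|, where f(10) = φ((10 − m)/2)/2 and E|D| = s × √(2/π).

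- f(10) = 0.3867/2 = 0.1933 for m = 10.5; 0.3521/2 = 0.1760 for m = 11.
- E|D| = 0.1596 for s = 0.2; 0.3989 for s = 0.5.

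Net change in the share below 10 g/dL = Φ((10 − m)/√(4 + s²)) − Φ((10 − m)/2).

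| m | s | Changing sides | Net change in share below 10 g/dL |
|---|---|---|---|
| 10.5 | 0.2 | 3.1% | 0.4018 − 0.4013 = 0.0005 |
| 10.5 | 0.5 | 7.7% | 0.4042 − 0.4013 = 0.0029 |
| 11 | 0.2 | 2.8% | 0.3094 − 0.3085 = 0.0009 |
| 11 | 0.5 | 7.0% | 0.3138 − 0.3085 = 0.0053 |

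Simulation agrees: 3.1% and 7.6% for m = 10.5, and a range of 2.8% to 7.6% over both means. So about 3 to 8 in every 100 non-transfusion-dependent subjects move in or out, while the number included changes by about 0.05 to 0.5 per 100. The shares are somewhat high for subjects under the minimum rule, for whom the 4-hour value does not always apply.

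**The case against.** The strongest reply is that the intent is plainly pre-dose. Sections 7.1 and 8.1 both say so, baseline hemoglobin is a listed baseline characteristic, and a programmer would probably take the pre-dose value. The intent is credible, but the sentence that governs this endpoint says otherwise and takes precedence over 8.1. If pre-dose is meant, the text should say it.

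It is also fair that part of the chain is inferred. The 4-hour draw is described under thrombocytopenia management, the Operations Manual section it cites is not in the text reviewed, and Appendix D has one hematology tick for Week 1 Day 1. That this draw yields a recorded hemoglobin value is an inference from its being called a hematology sample and from hemoglobin's place among the key laboratory parameters in SAP 9.3. This remains an assumption.

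On size, the calculation treats the pre-dose value as free of error. It has its own measurement noise, so without a drug effect either sample classifies subjects about equally well. This stands and limits the practical consequence. A reader might multiply the percentages by 230. That would overcount, because transfusion-dependent subjects do not depend on hemoglobin and some others use a minimum.

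A reader might also infer that the safety tables share the problem, because SAP 9.3 says of same-day values that "the minimum grade will be selected as the value for that day for baseline values". The rest of 9.3 does not support that. It places baseline before the first dose, defines the baseline grade by the dose and not its date, and takes the maximum grade from values collected after the first dose. The 4-hour sample is already post-baseline there, and the minimum-grade rule only chooses among values that qualify as baseline.

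**Conclusion.** Wrong as written. Followed literally, SAP 8.4.1.4 makes a post-dose hemoglobin the baseline for an endpoint in the confirmatory sequence, against the SAP's own pre-dose rules. This rests on the 4-hour panel reporting hemoglobin, and it applies to subjects who are not transfusion-dependent, with the minimum rule limiting it for those transfused within 4 weeks.

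The likely effect is modest: about 3% to 8% of non-transfusion-dependent subjects changing sides of the 10 g/dL line under the assumed values, mostly cancelling in net count. Changes at the 2 g/dL threshold are possible but would need further assumptions, so they are not sized here.

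A reader might infer that the anemia comparison is biased between arms, or that the type I error of the sequence is compromised. The documents do not support either. They describe no effect of navitoclax on hemoglobin at 4 hours; the acute mechanism they describe is platelet apoptosis. The primary endpoint does not use hemoglobin and is unaffected.

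**What to change.** In both baseline hemoglobin definitions of SAP 8.4.1.4, replace the date limit on the hemoglobin value with the limit used in 8.1: the last non-missing value drawn before the first administration of study drug, judged by date and time. Keep the existing randomization clause for untreated subjects. SAP 9.3 needs no change.

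The cost is one phrase in two sentences. It requires the collection time of the Day 1 samples, which is needed in any case to tell the pre-dose and 4-hour draws apart. Sample size, alpha and the testing order do not change.

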- A platelet count obtained approximately 24 hours (± 1 hour) post transfusion.

Management of Neutropenia

There is a potential for clinically significant neutropenia given the toxicity profiles of both ruxolitinib and navitoclax. The management of neutropenia guidelines, as listed in [Table 1](#) and below, should be implemented for all subjects unless previously discussed and approved with the AbbVie TA MD/SD.

- For Grade 3 neutropenia in addition to interruption as listed in [Table 1](#), support with G-CSF and/or prophylaxis with antibiotics may be considered at the discretion of the investigator.
- For Grade 4 neutropenia in addition to interruption as listed in [Table 1](#), support with G-CSF and/or prophylaxis with antibiotics may be considered at the discretion of the Investigator. If, in the opinion of the investigator, ruxolitinib dose can be resumed prior to recovery of ANC $\geq 1.0 \times 10^9/L$ or needs a dose reduction, consultation with the AbbVie TA MD/SD is necessary.

At any time during the study, if the subject presents with febrile neutropenia, navitoclax/placebo and ruxolitinib, if applicable, should be interrupted until resolution of the fever or infection.

Table 1. Dose Adjustment Guidelines for Thrombocytopenia and Neutropenia

 • After navitoclax/placebo and/or ruxolitinib dose modification, platelet counts should be rechecked approximately 7 days or sooner as clinically applicable until at least 2 consecutive laboratory values indicate stable platelet count. • If treatment is interrupted for platelet count $< 50 \times 10^9/L$, recheck platelets approximately every 2 to 3 days until recovery of platelets to $\geq 50 \times 10^9/L$. • Navitoclax/Placebo Dose levels for daily dosing: 200 mg, 150 mg, 100 mg, 75 mg, or 50 mg. 		
Hematology Results	Navitoclax/Placebo	Ruxolitinib per approved local label
Dose Modification for Thrombocytopenia		

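### For transfusion-independent subjects the SAP looks back 4 weeks for transfusions when setting baseline hemoglobin but only 2 weeks when scoring response, and one unconfirmed value is enough, so anemia responses can arise with no change since before treatment

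*SAP*

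**What the plan says.** SAP 8.4.1.4 splits the anemia endpoint by baseline transfusion status.

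- **Transfusion-independent subjects with baseline hemoglobin below 10 g/dL:** response is a 2 g/dL "increase in hemoglobin from baseline without receiving any PRBC transfusion within 2 weeks". The same sentence excludes erythropoietin use, there with a 4-week window. The section asks for no second value, minimum duration or visit window, and does not restrict the analysis to scheduled samples. It also does not say whether the 2 weeks run before the value, after it, or both. Values drop out only beyond 30 days after last dose, after confirmed progression, or once post-study treatment starts. Protocol 7.3 counts a response at any time during the study.
- **Baseline hemoglobin:** a special rule applies "For subjects who receive PRBC transfusion within 4 weeks on or prior to the date of the first dose of study drug". Baseline is then the lower of two values: "the baseline hemoglobin value is defined as the minimum of the hemoglobin value collected prior to the transfusion, if available", with the most recent pre-dose value as the other.
- **Transfusion-dependent subjects:** response requires "a period of at least 12 consecutive weeks without PRBC transfusion after the first dose of study drug".

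Anemia response is the third key secondary endpoint in Protocol 7.6 and step 4 of SAP Table 1. It is tested at two-sided 0.05 at the primary analysis. Section 8.4.1.4 names no sensitivity analysis for it, only separate summaries by baseline transfusion status.

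**The concern.** The section handles the same intervention in two ways. When baseline is set, a transfusion in the preceding 4 weeks leads to the lower value being used. When response is scored, a transfusion 15 days old is ignored. A value still raised by donor cells can then be compared with a baseline from which that effect has been removed. A subject who starts transfusion independent and is transfused on study can also be scored as improved once 2 weeks have passed. Because one value at any time is enough, measurement and biological noise get a fresh chance at every draw.

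Fibrosis, OS, LFS, fatigue and physical functioning all sit below this endpoint in the fixed sequence. False responders spread over both arms shrink a real difference and can close the gate. If they were unequal between arms, they could distort the comparison.

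**Working it through.** The plan states no expected anemia response rate and no power for this endpoint, so there is no figure to reproduce.

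**1. Worked case under the rule as written.** The hemoglobin values are illustrative; the rules are those of SAP 8.4.1.4, and the Day 2 draw is in Protocol Appendix D.
- Transfusion on Day -14; the subject does not meet the transfusion-dependence definition.
- Pre-transfusion hemoglobin 7.5 g/dL, last pre-dose value 9.5 g/dL.
- Baseline = min(7.5, 9.5) = 7.5, which is below 10, so the subject is transfusion independent and evaluable.
- Day 2 value 9.5: change = 9.5 − 7.5 = +2.0. There is no Day 0, so Day -14 to Day 2 is 15 days, outside the 2-week exclusion.
- Result: responder on Day 2, with hemoglobin unchanged since before the first dose.

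With a 4-week window, Day 2 (15 days), Week 2 Day 1 (21 days) and Week 3 Day 1 (28 days) are all excluded. Confirmation alone would not help: 9.5 again at Week 2 Day 1 would confirm the response under the 2-week rule.

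**2. Carry-over from an on-study transfusion.** Assumptions, not in the documents: 1 g/dL per unit, lost linearly over L = 45 to 90 days; within-subject SD σ = 0.5 to 0.7 g/dL.
- Residual at day d = units × (1 − d/L).
- P(observed rise ≥ 2) = 1 − Φ((2 − residual + prior fall)/(σ√2)).

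| Units | Day | Residual, g/dL | No prior fall | 1 g/dL prior fall |
|---|---|---|---|---|
| 2 | 15 | 1.33 to 1.67 | 17% to 37% | 0.9% to 8.9% |
| 3 | 15 | 2.00 to 2.50 | 50% to 76% | 8% to 31% |

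The last column is the more realistic one for a subject who has worsened enough to need transfusion. At day 29, with no prior fall, two units still cross in 3% to 26%, and three units at L = 90 leave 3 × (1 − 29/90) = 2.03 g/dL, about 51%. A 4-week window reduces carry-over but does not abolish it.

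**3. Single-value noise.** Scheduled post-dose hematology to Week 25 (Protocol 6.2 and Appendix D): 4 hours after first dose, Day 2, and Weeks 2, 3, 5, 7, 9, 13, 17, 21 and 25, which is 11 draws. For one draw, P = 1 − Φ(2/(σ√2)): 0.2% at σ = 0.5 and 2.2% at σ = 0.7. Simulating 11 independent draws against one noisy baseline, with no true change:

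| Assumed σ, g/dL | Any one value | Two consecutive values |
|---|---|---|
| 0.5 | 2.0% | 0.1% |
| 0.7 | 13.5% | 2.2% |
| 0.8 | 21.3% | 4.5% |

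Independence overstates this somewhat. With serially correlated errors (σ = 0.7, 7-day correlation constant, 10 draws) the single-value rate is 10.9%, and 1.9% with two consecutive scheduled values.

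**4. Effect on the contrast.** If a fraction f of true non-responders is falsely scored in both arms, the observed rate is p + (1 − p)f and the observed difference is (pA − pB)(1 − f). With f from 2.0% to 21.3%, the difference keeps 98% to 79% of its true size.

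**5. Unequal sampling.** Suppose 23 draws in Arm A, 11 in Arm B, 50 transfusion-independent subjects per arm and no true effect (all assumed). The chance of a false win for Arm A, nominally 2.5%, is about 3% at σ = 0.5, 14% at 0.7 and 17% at 0.8. With equal draws it stays at or below about 2.5%. Now suppose 20 draws against 10, with Arm A hemoglobin 0.25 g/dL lower (assumed). False responders, A against B, are about 1.1% v 1.9% (σ = 0.5), 4.9% v 6.2% (0.6) and 11.7% v 12.9% (0.7). The sign reverses.

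**The case against.** A reader might infer that the rule favours Arm A: navitoclax lowers platelets, Protocol Table 1 orders extra counts, and more counts mean more chances to cross 2 g/dL. The documents do not support that as a finding. For thrombocytopenia, Table 1 asks sites to "recheck platelets approximately every 2 to 3 days until recovery of platelets to" the stated level and otherwise to recheck platelet counts. Only the neutropenia rows call for hematology labs, so the extra hemoglobin values depend on full counts being run. Table 1 also applies to placebo subjects and to ruxolitinib, which causes thrombocytopenia itself. No draw counts by arm are given. Protocol 2.1 lists anemia among the most common Grade 3 or higher events with the combination, and step 5 of the working shows that a small hemoglobin deficit in Arm A turns the direction round.

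Other points on that side also carry weight. Transfusions before first dose should be balanced by randomization, so the worked case adds false responders to both arms rather than to one. The two response criteria address different patients and need not share a window. The endpoint is described as following IWG criteria, which the documents do not reproduce, so whether the SAP departs from them cannot be judged here. And this gate matters only if the three tests above it succeed.

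None of this removes the mismatch within 8.4.1.4. The erythropoietin exclusion in the same sentence is 4 weeks, as is the baseline transfusion look-back; only the post-baseline transfusion window is 2 weeks. The worked case follows from the text without any distributional assumption.

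**Conclusion.** The inconsistency is real, and it can produce a response where nothing has changed since before treatment. That part rests on the SAP's wording alone. The frequency of such cases is unknown, because the documents do not say how many transfusion-independent subjects are transfused shortly before or during treatment. The noise and carry-over sizes rest on assumed SDs, rise per unit and loss rates; at σ = 0.5 the noise effect is small (about 2%), at 0.7 to 0.8 it is not. The expected consequence is mainly dilution of the treatment contrast at step 4 of the sequence. A differential effect between arms is possible in either direction and should not be claimed from these documents.

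**What to change.** In SAP 8.4.1.4, for transfusion-independent subjects:

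1. State that the transfusion-free window runs before the hemoglobin value, and set it to 4 weeks, matching the section's own baseline and erythropoietin windows.
2. Require the 2 g/dL rise to be confirmed at the next scheduled visit, with no transfusion in between. At minimum, report this confirmed, scheduled-visit-only version as a pre-specified sensitivity analysis.
3. If the main rule changes, keep the current rule as a sensitivity analysis.

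The cost is SAP wording and programming; no visit or sample is added. Response rates will be somewhat lower in both arms. The confirmation interval will vary with visit spacing, from 1 week early on to 12 weeks after Week 25, and the SAP should say so. Some carry-over remains: a transfusion 28 days before first dose still resets baseline, yet Week 2 Day 1 is 28 + 7 = 35 days later and outside the new window.
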